7.2. Conventions

Unless otherwise specified, the following conventions will be applied to all analyses:

- 1 year = 365.25 days. Year is calculated as (days/365.25) rounded up to 1 significant digit;

- 1 month = 30.4375 days. Month is calculated as (days/30.4375) rounded up to 1 significant digit;
- Age will be calculated as the integer part of (date of randomization – date of birth + 1)/365.25;
- 1 pound = 0.454 kg;
- 1 inch = 2.54 cm;
- Time to event or duration of event endpoints will be based on the actual date rather than the associated visit date;
- Missing efficacy or safety data will not be imputed unless otherwise specified;
- For laboratory results collected as < or > a numeric value, 0.000000001 will be subtracted or added, respectively, to the value;
- For safety analyses, percentages will be calculated based on the number of patients in the analysis population in each treatment group;
- For by-visit observed data analyses, percentages will be calculated based on the number of patients with nonmissing data as the denominator unless otherwise specified;
- For time-to-event right-censored data, the summary statistics and descriptions will include Kaplan-Meier plots and/or life tables;
- For other continuous endpoints, the summary statistics will include mean, standard deviation, median, and range (minimum and maximum);
- For categorical endpoints, the summary statistics will include counts and percentages;
- Medical history will be coded using the Medical Dictionary for Regulatory Activities (MedDRA);
- Prior therapies and concomitant medications will be coded using the World Health Organization (WHO) Drug Dictionary.

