5. SAMPLE SIZE CONSIDERATIONS

The following assumptions are used in determining the sample size calculation for the MFS endpoint:

- 2:1 enzalutamide to placebo treatment allocation;
- An increasing nonuniform accrual of 0.25 patients per month per site with maximum accrual of 63 patients per month;
- For MFS a target hazard ratio of 0.72 at a 2-sided significance level of 0.05 with 90% power. Under an exponential model assumption, the target difference in Kaplan-Meier estimated median is 9 months (24 months versus 33 months). The median MFS of 24 months for the placebo group is based on published data.²

A total of 440 events provide 90% power to detect a target hazard ratio of 0.72 based on a 2-sided log-rank test and the overall significance level of 0.05. A sample size of approximately 1305 patients (870 enzalutamide and 435 placebo) will achieve 440 events. Approximately 10% of patients enrolled are expected to be lost to follow-up, will be found to have metastatic disease at study entry, or will have events censored due to required analytical methods, so approximately 1440 patients (960 enzalutamide and 480 placebo) will be enrolled. The time from date of first randomization until 440 MFS events are observed is estimated to be approximately 43 months.

Approximately 500 PSA progression events are expected at the time of the single MFS analysis. Based on a hazard ratio assumption of 0.60, this endpoint will have >95% power at a 2-sided significance level of 0.02 (see [Section 9.7.1](#) for details on multiplicity adjustments on key secondary endpoints).

Approximately 360 new antineoplastic therapy events are expected at the time of the single MFS analysis. This endpoint will have 80% power to detect a hazard ratio of 0.70 at a 2-sided significance level of 0.02 (see [Section 9.7.1](#) for details on multiplicity adjustments on key secondary endpoints).

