9.5. Extent of Exposure and Compliance of Study Drug

Data from patients in the safety population will be used to summarize the extent of exposure, compliance, and dose modification of study drug by treatment group as treated.

Treatment duration, total number of capsules taken, and percent overall compliance rate will be calculated and summarized by treatment group as treated. Treatment duration will be calculated as (date of last dose of study drug – date of first dose of study drug + 1). For patients who are continuing study drug at the analysis cutoff date, the last known date of study drug taken will be used as date of last dose of study drug. Treatment duration will be summarized both as a continuous measure and a categorical measure (≤ 3 months, 3 to < 6 months, 6 to < 12 months, ≥ 12 months). Number of capsules taken will be calculated based on the number of capsules dispensed at all study visits minus the number of capsules indicated as returned. The total cumulative dose in milligrams (mg) will be calculated as (40 mg \times number of capsules taken), as each capsule is equivalent to 40 mg of the study drug or placebo.

Percent overall compliance rate will be defined as the number of capsules taken during the study divided by the expected number of capsules, multiplied by 100. Capsules from bottles not returned will be subtracted from the number of capsules taken and the expected number of capsules in calculating percent overall compliance rate. Each patient will be taking 4 capsules each day while on study treatment. A patient's expected number of capsules will

be calculated as $[4 \times (\text{date of last dose prior to data cutoff date} - \text{date of first dose of study drug} + 1)]$. However, for subjects who have dose modifications (eg, dose reduction or dose withholding), the expected number of capsules will be calculated according to the dose modification. Percent overall compliance will be summarized both as a continuous measure and a categorical measure in increments of 20%.

Patients with at least 1 dose modification (including dose reduction and dose withholding) and the reason for the dose modifications will be summarized by treatment group as treated.

A data listing will be provided to present dose administration, modifications, and the derived compliance variables.

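### The SAP's default conversion of days to months and years rounds up to one significant digit; read literally it distorts reported durations and possibly patient-years, though no test result or exposure category

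*SAP*

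**What the plan says.** SAP 7.2 opens its list with a scope statement: "Unless otherwise specified, the following conventions will be applied to all analyses". Two items then define the time units: "Year is calculated as (days/365.25) rounded up to 1 significant digit" and "Month is calculated as (days/30.4375) rounded up to 1 significant digit". Both are worded as calculation rules, not display rules, and nothing elsewhere in the SAP corrects them.

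Some variables have their own rule and so escape the default:

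- SAP 7.1 defines treatment duration in months as the day count divided by 30.4375, with no rounding step.
- SAP Section 2 gives PSA doubling time its own formula.
- SAP 7.2 itself takes the integer part for age.

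Other quantities have no rule of their own: the Kaplan-Meier medians and the reverse Kaplan-Meier follow-up in SAP 9.7.2, time since diagnosis in months in SAP 9.4, and the patient-years denominator in SAP 9.8.1.

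SAP Section 5 works in months to one decimal place, with OS medians of 46 and 59.7 and a difference of 13.7.

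**The concern.** One significant figure is too coarse for durations of tens of months, and rounding up always pushes the value the same way. A programmer who followed the text exactly could report only 10, 20, 30 and so on for any duration of 10 months or more. One who assumed a slip would have to guess at two things: whether decimal places were meant, and whether a ceiling was intended. Two programmers could therefore produce different tables from the same plan. What is at stake is the accuracy of descriptive durations and, if years are rounded patient by patient, the time-adjusted adverse event rates.

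**Working it through.** **1. The plan's own figure, which does not use the rule.** SAP Section 5 states: "A total of 440 events provide 90% power to detect a target hazard ratio of 0.72 based on a 2-sided log-rank test". The inputs are hazard ratio 0.72, two-sided alpha 0.05, power 90% and 2:1 allocation. The Schoenfeld formula gives

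events = (1.960 + 1.282)² / [(2/3)(1/3)(ln 0.72)²] ≈ 438.2, rounded up to 439.

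With 440 events the power is 90.1%. The stated figure reproduces, and no conversion of days to months enters it.

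**2. The literal rule on summary medians.** For a duration x, let k = floor(log10 x). The rule returns ceil(x/10^k) × 10^k. The design medians from SAP Section 5 serve as examples:

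| Median (months) | Literal rule |
|---|---|
| 24 (MFS, placebo) | 30 |
| 33 (MFS, enzalutamide) | 40 |
| 46 (OS, placebo) | 50 |
| 59.7 (OS, enzalutamide) | 60 |

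The MFS difference goes from 9 to 40 − 30 = 10 months. The OS difference goes from 13.7 to 60 − 50 = 10 months.

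**3. Rounding each patient's time first.** Under exponential times, S(t) = 0.5^(t/median).

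- Median 24: S(20) = 0.561 and S(30) = 0.420, so the median of the rounded times is 30.
- Median 33: S(30) = 0.533 and S(40) = 0.432, so it is 40.
- Median 46: S(40) = 0.547 and S(50) = 0.471, so it is 50.
- Median 59.7: S(50) = 0.560 and S(60) = 0.498, so it is 60.

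The stage at which rounding is applied does not change these results.

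**4. The one-decimal reading.** 24.0, 33.0 and 59.7 stay as they are. A ceiling at 0.1 month adds on average half a step, 0.1/2 = 0.05 months, or 0.05 × 30.4375 ≈ 1.5 days. Rounding to nearest removes this bias.

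**5. Patient-years.** SAP 9.8.1 divides event counts by patient-years and gives no conversion of its own. Under the literal rule a man followed for 1.2 years would count as 2 and one followed for 2.3 years as 3. The documents give no distribution of follow-up, so one is assumed: exponential durations with medians of 12 to 33 months, with and without uniform administrative censoring between 6 and 43 months. If each man's years are rounded and then summed, simulation gives:

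- literal rule: patient-years inflated by 20% to 27%, so rates are multiplied by 1/1.20 = 0.83 to 1/1.27 = 0.79, a fall of about 17% to 21%;
- one-decimal ceiling: patient-years inflated by 1% to 5%.

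If years are summed first and rounded afterwards, the distortion depends on the total. The SAP does not say which order applies.

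**6. Exposure categories.** SAP 9.5 groups treatment duration as "≤ 3 months, 3 to < 6 months, 6 to < 12 months, ≥ 12 months". With the unrounded SAP 7.1 formula, no duration moves between these groups.

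**The case against.** The strongest reply is that nobody would apply the rule literally. The SAP's own 59.7 and 13.7 months cannot be expressed to one significant figure, and a median of exactly 30 or 40 would be noticed at once. Loosely read, the phrase may mean no more than one decimal, with no ceiling intended. If a ceiling was intended at one decimal, about 1.5 days is negligible beside a 112-day scan interval, and it acts alike in both arms. Also, the MFS analysis is already done: SAP Section 2 reports the endpoint met at the 28 June 2017 cutoff, and SAP Section 8 plans no further primary analysis. All of this stands and keeps the point small. It does not make the rule correct as written, and the OS reporting, the exploratory updates planned with the later OS analyses, and the safety rates were still ahead.

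Three stronger readings are tempting, and the documents do not support them.

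- **Men would move between exposure categories.** This needs the general rule to be layered on the SAP 7.1 formula. That formula has no rounding step, and SAP 7.2 gives way to anything specified elsewhere.
- **Rounded months would tie event times and disturb the log-rank and Cox results.** The SAP does not state the analysis unit, but SAP 7.2 bases time-to-event endpoints on actual dates and nothing says that rounded months are analysed. In days, these results are untouched.
- **The trial's MFS medians would be reported as 30 and 40.** The 24 and 33 months are design assumptions, not results. SAP 9.7.2 does not name the unit for medians; months is a reasonable inference from Section 5.

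**Conclusion.** The point holds as a minor wording error in an operative default rule. Literally applied, it would misstate reported medians by up to several months (24 as 30, 33 as 40, 46 as 50, 59.7 as 60). If years were rounded per patient, it would lower time-adjusted adverse event rates by roughly 17% to 21% under the assumed follow-up distributions. On the more likely one-decimal reading, what remains is an upward shift of about 0.05 months on average and a 1% to 5% inflation of patient-years if rounded per patient. Treatment-duration categories, event counts and power are unaffected, as are the log-rank and Cox results provided times are analysed in days. The realistic effect is confined to descriptive durations and possibly patient-years.

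**What to change.** Replace the two lines in SAP 7.2 with: months = days/30.4375 and years = days/365.25, analysed, summed and categorized unrounded; rounded to the nearest 1 decimal place for display only.

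This agrees with the treatment-duration formula in SAP 7.1, settles the order of operations for patient-years, and removes the ceiling. It costs two lines of SAP text and changes nothing in the design, alpha allocation, event targets or data collection.

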6.2. Safety Population

The safety population is defined as all randomized patients who receive at least 1 dose or partial dose of study drug (enzalutamide or placebo). Unless otherwise specified, all safety analyses will use the safety population according to the actual treatment received (not the treatment assigned).

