9.8.1. Adverse Events

The severity of all adverse events is to be evaluated by the investigator based on the National Cancer Institute (NCI) Common Terminology Criteria for Adverse Events (CTCAE) version 4.0 or later. All adverse events will be coded to preferred term (PT) and system organ class (SOC) using MedDRA 14.1 or higher.

Treatment-emergent adverse events (TEAEs) are adverse events that started or worsened in severity during the treatment-emergent period.

Patients with multiple occurrences of events for a given PT, SOC, or overall will only be counted once at the worst severity and strongest relationship to study drug for each PT, SOC and overall, respectively.

Adverse event time-adjusted rates will be calculated as the number of occurrences of event divided by the number of patient-years of treatment-emergent surveillance for each treatment group. Patients can have more than one occurrence of each event.

Tabular summaries including numbers and percentages of the following adverse events will be provided:

- TEAEs;
- Serious TEAEs;
- TEAEs by SOC and PT;
- TEAEs by SOC, PT, and maximum severity;
- TEAEs by SOC, PT, and strongest relationship to study drug;
- TEAEs by decreasing frequency of PT;
- TEAEs of grade 3 or higher;
- TEAEs of grade 3 or higher by SOC, PT, and relationship to study drug;
- TEAEs related to study drug (judged by the investigator) by SOC, PT, and severity;
- TEAEs leading to study drug discontinuation;
- TEAEs leading to study drug discontinuation by SOC, PT, and severity;
- TEAEs leading to dose reduction;

- TEAEs leading to dose reduction by SOC, PT, and severity;
- TEAEs leading to dose interruption;
- TEAEs leading to dose interruption by SOC, PT, and severity;
- Serious TEAEs by SOC, PT, and severity;
- Serious TEAEs by SOC, PT, and relationship to study drug;
- Serious TEAEs that caused study treatment discontinuation by SOC and PT;
- TEAEs leading to death by SOC and PT.

Additionally, Kaplan-Meier methods will be used to display the time to the first grade 3 or higher TEAEs by treatment group.

Subgroup and supplemental tabulations of TEAEs by categorized treatment group, grade 3 and higher TEAEs by categorized treatment group, and serious TEAEs by categorized treatment group will be created as shown in Table 5.

Table 5: Subgroup and Supplemental Tabulations of Treatment-Emergent Adverse Events

Group Variable	Subgroups	Definition

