Study Day Cut Points	
  ≤ 60 days after initiation of study drug  ≤ 180 days after initiation of study drug  ≤ 365 days after initiation of study drug  > 365 days after initiation of study drug 	
Adverse events will be assigned to day categories based on the treatment day of the start date (or worsening date) of the adverse event. Study days after initiation of study drug use the study day computations presented in Section 7.1.

Age (years)	
  < 65  ≥ 65  < 75  ≥ 75 	-
Baseline Body Mass Index	
  ≤ Median  > Median 	-
Geographic Region	
  North America  European Union  Rest of the World 	Defined in Appendix 2 .
History of Cardiovascular Disease	
  Yes  No 	Defined in Appendix 2 .

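### The > 365-day adverse-event row in SAP Table 5 is divided by the whole safety arm, so late incidence among men still exposed is understated and the comparison between arms reflects unequal exposure

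*SAP*

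**What the plan says.** SAP 7.2 opens its conventions with "Unless otherwise specified, the following conventions will be applied to all analyses". One of them reads "For safety analyses, percentages will be calculated based on the number of patients in the analysis population in each treatment group". SAP 6.2 defines the safety population as every randomized patient who took at least part of one dose.

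SAP 9.8.1 then plans "Subgroup and supplemental tabulations of TEAEs by categorized treatment group", with parallel tables for grade 3 or higher and for serious events, laid out in Table 5. Three of the Table 5 time categories (up to 60, 180 and 365 days) start at first dose. The fourth is "> 365 days after initiation of study drug". No denominator is given for any of them, so the 7.2 default applies.

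SAP 7.1 ends the treatment-emergent period at last dose plus 30 days, or the day before a new antineoplastic treatment if that is earlier.

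Three other analyses bear on exposure:
- SAP 9.8.1: "Adverse event time-adjusted rates will be calculated as the number of occurrences of event divided by the number of patient-years of treatment-emergent surveillance". These are given by arm, and a split at day 365 is not mentioned.
- SAP 9.8.1: "Kaplan-Meier methods will be used to display the time to the first grade 3 or higher TEAEs by treatment group".
- SAP 9.8.1.1: Kaplan-Meier time to first occurrence for the events of special interest, if there are enough events.

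**The concern.** Every dosed man is at risk at the start of the three cumulative categories, so the whole arm is a natural denominator there. The > 365-day row differs. A man who left the treatment-emergent period in month 4 cannot have an event in it but still dilutes its percentage.

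The dilution is unlikely to be equal between arms. SAP 2 keeps patients on drug until radiographic progression, and the trial is designed to delay progression on enzalutamide. A higher expected proportion of the placebo arm will therefore have stopped before day 365. Enzalutamide men who pass day 365 are also expected to stay on longer, so each has more time in which to have a late event.

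This is the only Table 5 category that isolates late-onset events, for a drug that asymptomatic men may take for years. Read at face value, it gives too low an incidence for men still on treatment and a between-arm difference that can arise from exposure alone.

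**Working it through.** **The plan's own figure.** The MFS medians feed the exposure calculation, so the sizing they belong to was checked first. Schoenfeld events for HR 0.72, two-sided 0.05, 90% power, 2:1 allocation: (1.960 + 1.282)² / [(2/3)(1/3)(ln 0.72)²] = 10.507 / 0.02398 = 438.2, rounded up to 439, against 440 stated. Power at 440 events is 90.1%. The figure reproduces.

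**Inputs from the SAP.**
- Section 5: exponential model, placebo median 24 months, HR 0.72, so the enzalutamide median is 24/0.72 = 33.3 months (stated as 33); 960 and 480 patients; at most 63 patients per month; 440 events at about 43 months.
- Section 7.1: 30-day tail = 30/30.4375 = 0.99 months.

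**Assumptions; the documents give no figures.**
- MFS medians stand in for time on treatment.
- Accrual is uniform over 23 months (1440/63 = 22.9), with cutoff at month 43.
- After month 12 the true first-event rate is 10 per 100 patient-years in both arms.

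**Step 1: share at risk past month 12.** S = exp[−ln 2 × (12 − 0.99)/median].
- Placebo: 72.75%, about 349 of 480.
- Enzalutamide: 79.5%, about 763 of 960.

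Everyone has at least 43 − 23 = 20 months to cutoff, so no one is lost to the cutoff before month 12. About 131 placebo and 197 enzalutamide men have left by then.

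**Step 2: probability of a late event among those at risk.** Let λ = 0.10/12 per month, h = ln 2/median and k = h + λ. Cutoff falls uniformly between 8 and 31 months after month 12, so

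P = λ × [1/k − e^(−8k)(1 − e^(−23k))/(23k²)].

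- Placebo: k = 0.03721; bracket = 26.87 − 13.41 = 13.47 months; P = 11.2%.
- Enzalutamide: k = 0.02913; bracket = 34.33 − 19.82 = 14.51 months; P = 12.1%.

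**Step 3: the same events on three denominators.**

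| Denominator | Placebo | Enzalutamide | Ratio |
|---|---|---|---|
| Whole arm (S × P) | 8.2% | 9.6% | 1.18 |
| At risk past month 12 (P) | 11.2% | 12.1% | 1.08 |
| Patient-years after month 12 | 10.0 per 100 | 10.0 per 100 | 1.00 |

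The whole-arm figure is below the at-risk figure by 1 − S: 27% on placebo and 20% on enzalutamide. The false ratio has two factors: 1.09 from the share reaching month 12 (79.5/72.75) and 1.08 from longer time at risk afterwards. An at-risk denominator removes only the first. Patient-years remove both.

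**Range (assumed; enzalutamide median 33 months).** The whole-arm ratio is 1.17 with no other stopping, and stays 1.17 with a further 5% or 10% per year stopping in both arms. With 5% per year it is 1.42 if the placebo median time on treatment is 18 months and about 2.04 if it is 12 months. The matching at-risk ratios are 1.07 to 1.08 at the planned medians, then 1.17 and 1.36.

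**The case against.** **The SAP already handles unequal exposure.** In part. Patient-year rates and Kaplan-Meier displays are planned, so a reader who infers that late safety rests on this table alone would be wrong. But the rates are per treatment group over the whole treatment-emergent period and count repeat occurrences, so they do not isolate late onset. The Kaplan-Meier displays cover first grade 3 or higher events and, conditionally, events of special interest. None gives a corrected figure for the > 365-day tabulations of all TEAEs or serious TEAEs.

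**The whole-arm percentage is legitimate.** It is: the share of treated men who have an event after day 365 is a valid unconditional quantity. It is not the risk among men still taking the drug, and the table does not show how many men could contribute. The at-risk percentage has its own weakness, because it conditions on staying on treatment for a year, which happens after randomization.

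**The exposure proxy is weak.** This stands. Protocol 3.1 and 5.3 let study drug continue after radiographic progression if judged beneficial, and men also stop for adverse events or by choice. The size is illustrative. With equal exposure the false ratio would disappear, but the dilution would remain.

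**A stronger reading on subgroups.** A reader might infer that the age, BMI, region and cardiovascular-history tables also divide by the whole arm. No passage says so. The 7.2 rule yields where something else is specified, those tables are planned by categorized treatment group, and an analyst would ordinarily use arm-by-subgroup counts. The phrase is not defined, but that is no evidence of a wrong denominator.

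**Conclusion.** The point holds for one row. Under the 7.2 default, the Table 5 > 365-day percentage includes men who can no longer contribute an event. With the planned medians as a proxy for exposure and an equal assumed late rate, late incidence among exposed men is understated by about 27% on placebo and 20% on enzalutamide, and a true rate ratio of 1.00 prints as 1.18. The ratio is larger if placebo exposure is shorter than assumed. Actual time on treatment and late-event rates are not in the documents.

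Two further inferences are not supported. The distortion does not hide a drug excess: if placebo men stop earlier, the comparison is tilted against enzalutamide. Nor do more placebo men leave early as a count: with 2:1 allocation, about 131 placebo and 197 enzalutamide men have left by month 12 in this calculation. Only the expected proportion is higher on placebo (27% against 20%).

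No efficacy result or error rate is affected. This is an inexpensive improvement to a supplemental safety table.

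**What to change.** For the > 365-day row of SAP Table 5 only:

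1. Print, by arm, the number of safety patients whose treatment-emergent period extends beyond treatment day 365.
2. Use that number as the denominator. The whole-arm percentage may be kept alongside.
3. Add events per patient-year of treatment-emergent surveillance after day 365. This is the figure that removes the exposure distortion; step 2 alone would still leave a ratio of about 1.08.

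The three cumulative categories need no change.

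The cost is a sentence in SAP 7.2 or 9.8.1 and a revised table shell; no new data are needed. There are three downsides. Late percentages will be higher than under the current rule. The at-risk percentage describes men who stayed on treatment for a year, and a footnote should say so. And because SAP 2 records that all patients were unblinded after the 28 June 2017 cutoff, the added figures should be labelled supplemental.
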